8. STUDY PARTICIPANTS

8.1 Study Setting

This is a single centre, prospective, interventional, feasibility study. All patients who are found to have operable oesophageal cancer will be offered to be involved in the study. Patients will be seen in the specialist upper GI cancer clinic following MDT discussion at which point they will be informed of the study and given information to read. Consent for involvement in the study will be taken either at pre-assessment clinic, on the day of staging laparoscopy, or on the day of oeophagectomy. Potential participants will have the opportunity to ask questions at any appointment or by contacting the research team directly. All participants will then be monitored closely as is standard for patients undergoing this type of operation.

8.2 **Overall Description of Study Participants**

Participants with oesophageal cancer who are undergoing elective oesophagectomy.

8.3 Eligibility Criteria

Inclusion Criteria

- 1. NHS patients undergoing elective minimally invasive oesophagectomy.
- 2. Aged 18 years and above.
- 3. Able to provide informed consent

Exclusion Criteria

1. Previous adverse reaction to BioGlue or one of its constituent ingredients

9. SAMPLING

All patients who are referred to the QAH and are found to have a diagnosis of oesophageal cancer which is deemed amenable to surgery following MDT discussion will be given the opportunity to take part in the trial.

Currently, around 70 oesophagectomies are performed at our centre annually. Recruitment is estimated to be completed within 12 months.

10. STUDY PROCEDURES

10.1 Recruitment

Patients will be recruited from a single site, Queen Alexandra Hospital. All elective patients who attend the Upper GI clinic at Portsmouth Hospitals NHS Trust having been found to have oesophageal cancer and are suitable for, and willing to undergo, oesophagectomy will be approached to take part in the study.

These patients will be approached for recruitment whilst attending the Upper GI clinic.

10.2 Screening and Enrolment

Patients will be screened for eligibility at first surgical visit for this study using inclusion & exclusion criteria (9.3) on a screening log (online). If they are potentially eligible, the surgeon will introduce the option of joining this study during this consultation to the patient, giving them the participant information sheet.

All patients will undergo standard pre-operative assessment of fitness e.g. CPET and then diagnostic laparoscopy in the pre-operative period. They will have the opportunity to contact the research team in the time between their initial attendance in the clinic and the day of surgery. Additionally, they have the opportunity to ask questions in person when they attend for their diagnostic laparoscopy.

On the day of surgery patients will be enrolled onto the study. The research team will ascertain that the patient has understood what the study involves before consenting them. If the patient agrees to be included in this study, they will be asked to sign a consent form and a Case Report Form (CRF) with a Participant Study ID (initials+number) created at this point with a record made in the patient's notes and a standard letter to patient's GP.

10.3 Randomisation

In this feasibility study the patients will not be randomised. The intervention will be applied to all patients who consent.

10.4 Study Assessments

The baseline information will be collected on the CRF following informed consent. Data will include:

- (i) Socio-demographic variables: age, gender, work/hobbies involving physical activity
- (ii) Physical examination: weight, height, BMI,
- (iii) Medical history: ASA (American Society of Anaesthesiologists physical status classification), and co-morbidities, current medication and allergies;
- (iv) Clinical history/examination: symptoms and symptom duration, endoscopy/CT/ laparoscopic findings

Data collected during surgery will include:

- the date of surgery
- operation duration
- any difficulty in the application of the BioGlue specifically if there were areas at which the BioGlue was not able to be applied
- intra-operative complications
- any specific concerns about the perfusion or state of the gastric conduit or anastomosis
- any deviation from standard post-operative protocol

Following surgery patients will be admitted to ITU. They will be managed identically to patients who have not been included in the study, with initially continuous recording of the observations. Decisions about change in care or progression with diet or drains will be made by an appropriately experienced consultant surgeon. A standardised Enhanced Recovery Protocol is followed.

Progression in the post-operative phase will be based on the patients clinical and biochemical findings and if necessary guided by imaging.

Up until the day of discharge all patients will have at least once daily clinical review by the surgical team. The majority of anastomotic leaks occur fairly early in the postoperative phase and almost all before discharge. Following discharge from hospital patients will be followed up as standard with a phone call one week after discharge and then in the outpatient clinic at 2 and 6 weeks. In addition to normal postoperative follow up, participants in the study will all be seen at six-weeks following their surgery.

Assessment of technical feasibility will be done using qualitative methods consisting of short interviews with surgeons post-operatively which will be subsequently analysed. Specifically we are interested in the surgeons' views on difficulties with the product, acceptability and any suggestions for improving the product or surgical technique.

10.5 Discontinuation/Withdrawal of Participants from Study Treatment

Patients withdrawing consent from the study will continue to have data which has already been collected used in the post-operative analysis. Once the surgery has occurred, there is no option for the removal of BioGlue and patients will be managed in the standard way.

Any patient who does not undergo surgery will not be included in the trial. Where surgery is abandoned intraoperatively for a surgical or anaesthetic reason, prior to the formation of the anastomosis, the patient will be withdrawn from the trial. This situation will be exceptionally uncommon.

10.6 Definition of End of Study

The end of the study is 6 weeks post-operatively following the last patient's operation.

11. INTERVENTIONS

11.1 Description of Study Intervention / Treatment

The surgical procedure performed is routine other than the addition of the BioGlue (mixture of purified bovine serum albumin and glutaraldehyde) to the anastomosis using the laparoscopic applicator tip. Detailed description of the surgical technique is included as appendix 3.

The procedure is performed under general anaesthetic using keyhole surgery in two stages, by two Consultant Surgeons. In the abdominal stage the stomach is mobilized from its attachments and lymph node dissection performed. The gastric conduit is then constructed using the greater curve of the stomach and relies on the right gastroepiploic arcade for its blood supply. The distal oesophagus is then freed from the hiatus and visible attachments in the posterior mediastinum. A feeding jejunostomy is constructed prior to closing the abdomen and moving to the chest. In the thoracic stage oesophagus is mobilized from surrounding thoracic tissue, and gastric conduit delivered into the chest. Approximation of the conduit and the oesophagus is then assessed and when happy the oesophagus divided, and specimen removed through an extraction site.

The anastomosis is an end to side linear stapled gastro-oesophageal anastomosis. A bougie catheter is inserted down the oesophagus and an enterotomy is made onto the bougie on the distal, postero-lateral side using diathermy. The mucosa at this opening is then sutured with two stitches to prevent retraction. A gastrotomy is then created on the mesenteric side of the stomach at least 5cm from the tip of the conduit. The blades of linear stapling gun are inserted into the two enterotomies created, one in the oesophagus and one in the gastric conduit. The gun is fired creating a 3-4cm window between oesophagus and stomach, and the remaining enterotomy closed with two layers of sutures.

The BioGlue will then be prepared as per manufacturers instructions. The glue will be applied using the laparoscopic applicator tip to cover the closed enterotomy and staple lines of the gastro-oesophageal anastomosis. It will not be used to cover the staple line of the gastric conduit. Surgeons will aim to apply a 2-3mm thick coating of the BioGlue 5-10mm either side of the anastomotic suture/staple line, as advised by manufacturers. Great care will be taken to avoid application of BioGlue to other tissues in the thorax; such as placing unfolded saline soaked swabs in the operative field to catch any spillage. If this does occur, then it will be at the discretion of the operating surgeons as to whether to remove this BioGlue or not once hardened, as removal of the glue can damage the underlying tissues, and its application should not cause harm to the structures exposed during the procedure. Application of the BioGlue will be videoed and the file saved for study records.

11.2 Adherence to Study Treatment

The surgical steps and techniques will be standardised between all surgeons participating in this study as described above. All of the surgeons participating in the study are experienced Consultants in Upper Gastro-Intestinal Surgery, and routinely perform minimally invasive oesophagectomies. The Principal Investigator (PI) will initially demonstrate to the other surgeons taking part in the study how to assemble the BioGlue laparoscopic applicator and apply the BioGlue to the gastro-oesophageal anastomosis in the described manner. The PI

will then move to supervising the other surgeons applying the BioGlue to the anastomosis once they are familiar with the technique. When the PI is confident that a surgeon taking part in the study is competent to apply the BioGlue independently it will be signed off in the study competency log. All surgeons participating in this study are proficient in complex laparoscopic surgery and it is expected that they should all be able to attain competency early on in the study.

11.3 Accountability of the Study Treatment

The chief investigator is accountable for the study treatment. BioGlue is produced and distributed by Cryolife and the product will be kept and stored as per the manufacturer's instructions within the theatre complex at QAH.

11.4 Concomitant Medication / Therapies

Operative and post-operative analgesia and anti-emetics will be prescribed according to standard operative protocols. If the patient is readmitted for complications or further therapy, this will be recorded as an adverse event (AE) or serious adverse event (SAE).

12. ASSESSMENT OF SAFETY (IF APPLICABLE)

12.1 Definitions

Adverse Event:

Any untoward medical occurrence, unintended disease or injury, or any untoward clinical signs (including an abnormal laboratory finding) in participants, users or other persons concerned with the medical device. These may, or may not be, considered related to the investigational material (i.e. BioGlue), related procedure or comparator. If the AE is considered to have a reasonable causal relationship with the material, then it is considered to be an Adverse Device Effect (ADE).

To fully address the potential adverse events following oesophagectomy we must include the established complications from surgery. Participants would be at risk of these complications irrespective of whether they receive the intervention or not. They will all be considered an expected adverse event and include (2):

- Pneumonia.
- Atrial dysrhythmia.
- Anastomotic leak.
- Gastric conduit necrosis.
- Chyle leaks.
- Recurrent laryngeal nerve injury.

BioGlue's manufactures CryoLife, detail the potential local and systemic adverse effects of the device in their product literature. These complications are specific to the adjunctive use of BioGlue during soft tissue repair, and include:

- Failure of product to adhere to intended tissue.
- Application of adhesive to unintended tissue.

- Inflammatory and immune response.
- Allergic reaction.
- Mineralization of tissue.
- Local tissue necrosis.
- Damage to normal vessels or tissue.
- Blood vessel, bronchial or luminal obstruction.
- Thrombosis, thromboembolism and pulmonary embolism.

CryoLife provide reference to evidence in the literature of these events in experimental animal and human studies investigating its use on cardiac or pulmonary tissue. They do not provide any reference to its use or effects on the alimentary tract (7). Literature review as part of the protocol development has found a number of studies assessing its use and safety on the alimentary tract, none of which have reported these complications. Systematic review of the use of tissue adhesives in gastro-oesophageal anastomosis identified a number of studies in animals and humans (11). None of the above complications were reported; however, it must be noted that the only outcomes measured were collagen synthesis, bursting pressure and anastomotic leak. An RCT comparing the application of BioGlue to reinforce the staple line in stapled haemorrhoidopexy vs standard procedure, found it reduced post-operative complications. Participants who received BioGlue did not have any anastomotic leak, thrombosis, haemorrhage or anal stenosis; all of which occurred in the standard treatment group, and are potential complications detailed in manufactures instructions for use (17). A systematic review of tissue adhesives in gastro-intestinal anastomosis found a range of evidence from animal and human clinical studies, on a number of tissue adhesive products. BioGlue was investigated in 3 of the 48 studies. The review identified no local complications from any of the tissue adhesives, such as tissue damage, luminal stenosis/blockage, injury to nerves, blood vessels, heart or lung parenchyma, or intra-abdominal solid organs (20). All of these review articles highlight the variability between studies and poor overall quality of evidence. Nonetheless the potential complications discussed in the manufacturer's literature have not been found to be significant in any of these studies and provides reassurance that BioGlue is highly likely to be safe in this application.

Participants in the study are at risk of these reactions, however they are so uncommon we believe that with such a small study group it is unlikely to cause any of them harm. The manufacturers instruction for use provides warnings for use of BioGlue in certain situations to avoid these reactions:

- Could contact or obstruct circulating blood flow.
- Could obstruct circulating air or luminal fluid flow.
- Contact with nerves, eyes or unintended tissue.
- Not to be used in presence of infection and used with caution in contaminated areas.
- Exercise caution with repeated exposure due to hypersensitivity reaction. Sensitisation has been observed in animal studies.

We do not expect or intend to use BioGlue in any of these situations, thus minimising any risk of adverse reactions.

BioGlue contains material of animal origin, which may be capable of transmitting infectious agents. CryoLife, Inc. is a U.S. FDA-registered medical device establishment (Registration #

1063481) and human cells, tissues, and cellular and tissue-based product establishment. It is also certified to the international quality standards (ISO 13485:2016) for the design, manufacture, and distribution of tissues and medical devices. BioGlue has been developed and manufactured in accordance with these national and international standards to ensure such risks are minimised.

Any adverse event resulting from insufficiencies or inadequacies in the instructions for use, the deployment, the implantation, the installation, the operation, or any malfunction of the investigational medical device will be considered an adverse device effect.

Serious adverse event:

A serious adverse event is any untoward medical occurrence that:

- Results in death
- Is life-threatening

NOTE: The term "life-threatening" in the definition of "serious" refers to an event in which the participant was at risk of death at the time of the event; it does not refer to an event which hypothetically might have caused death if it were more severe.

- Requires inpatient hospitalisation or prolongation of existing hospitalisation,
- Results in persistent or significant disability/incapacity, or
- Is a congenital anomaly/birth defect.
- Other important medical events*

*Other events that may not result in death, are not life threatening, or do not require hospitalisation, may be considered a serious adverse event when, based upon appropriate medical judgement, the event may jeopardise the participant and may require medical or surgical intervention to prevent one of the outcomes listed above.

12.2 Reporting Procedures for Serious Adverse Events

A serious adverse event (SAE) occurring to participant should be reported to the REC that gave a favourable opinion of the study where in the opinion of the Chief Investigator the event was: 'related' – that is, it resulted from administration of any of the research procedures; and 'unexpected' – that is, the type of event is not listed in the protocol as an expected occurrence. Reports of related and unexpected SAEs should be submitted within 15 days of the Chief Investigator becoming aware of the event, using the NRES report of serious adverse event form.

12.3 Recording and Reporting Procedures for All Adverse Events

AEs will be recorded on the relevant section of the CRF.

Information recorded will include:

- date of onset
- severity

- frequency
- treatment provided
- assessment of causality with the device
- whether or not the AE was expected or unexpected

All AEs must also be documented in the patient's medical records and must be followed up until resolution. If the AE should result in any lasting secondary disease this will be recorded accordingly when completing the study.

The sponsor's SOP for the reporting of all Adverse Events will be followed in the timeline set out in this procedure.

13. DATA HANDLING AND RECORD KEEPING

13.1 Data Collection Forms

Once a patient is recruited, the data will initially be collected on a paper-based CRF kept securely in the research office when not used for data collection. It will be transcribed prospectively onto an online CRF. Source data/documents (i.e. patient notes) are kept within QAH as per standard procedure and can be accessed as required through the standard mechanisms. CRFs will be stored for a maximum of 15 years after the study has been completed.

13.2 Data Management

All study data will be entered on a bespoke Microsoft Access database. The participants will be identified by a study specific participant number and/or code in any database. The name and any other identifying detail will NOT be included in any study data electronic file. The database will be stored securely on a secure hospital file storage area network with automated backups and will be password protected.

Data variables will include basic demographic data, operative details including operative duration and details regarding the application of the glue, post-operative course and specifically any complications, AE and SAE.

The database will be maintained for 10 years following study completion.

14. DATA ANALYSIS

14.1 Description of Analysis Populations

Analyses will be as per intention-to-treat i.e. all participants will be included.

14.2 Analysis of Endpoints

Primary endpoints are qualitative outcomes and outside of the remit of a statistical analysis plan.

Secondary endpoints will be described appropriately for use in informing future controlled analysis.

Time to event outcomes (operative duration, time to discharge) will be presented with the number of events experienced and the median time to event.

Indicator variables where the outcomes takes an occurrence/non-occurrence status are Anastomotic leak rate (leak/no leak), All-cause mortality up to 6 weeks follow up (death/ no death), Unplanned return to ITU (return/no return), Unplanned return to theatre(return/no return), and Unplanned return to surgical high care unit (return/no return). In all cases the proportion in each category will be reported, along with the standard error for the proportion.

Categorical variables with more than one category (Clavien-Dindo scale of post-operative complications) will similarly be presented with the proportion in each category reported. The number of CT scans will be treated as a multi category categorical variable in this case, since the number of scans during the study is likely to be relatively low. The use of antibiotics will also be treated as a multicategory categorical variable, although as well as the proportion using each antibiotic, the median duration of use will also be reported.

14.3 **Procedure for Dealing with Missing, Unused and Spurious Data**

There will be no imputation of missing values.

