4. BACKGROUND AND RATIONALE

1. Oesophagectomy is the surgical treatment of oesophageal malignancy

The incidence of adenocarcinoma of the oesophagus has been observed to be rapidly increasing in the UK and the western world although incidence of squamous cell carcinoma of the oesophagus has been steadily declining. Cancer of the oesophagus (all types) is the sixth most common cancer in men and the ninth most common cancer in women worldwide with an observed six-fold increased incidence in men (8). The management of carcinoma of the oesophagus remains challenging (9). If a patient presents with malignancy which can be treated with curative intent, the surgical option is oesophagectomy. This was traditionally performed as an open operation but has progressed over the last 25 years and is now quite widely offered as a minimally invasive procedure – with laparoscopic and thoracoscopic stages (10). Within QA all oesophagectomies are undertaken with the aim of completion using minimally invasive techniques.

2. Anastomotic leaks are a major cause of perioperative morbidity and have a significant financial impact

One of the major risks of oesophagectomy is of a leak from the gastro-oesophageal anastomosis. Leak rates from the gastro-oesophageal anastomosis are quoted by NICE as 20%, which correlates with similar international figures e.g. The Dutch National database (1) (11). An anastomotic leak leads to prolonged in-hospital stay, can require an unplanned return to theatre, return to ITU and is associated with mortality as well as morbidity (2). Increases in mortality ranging from 18.2-35% have been quoted in the literature (12). As well as the distress, pain and other negative outcomes for the patients, the need for re-operation, return to ITU and increased length of stay come at significant financial cost. A Dutch team showed that a minor complication increases the cost of surgery for oesophageal cancer from an average of €59,167. Specifically, they showed the average cost of a patient who had suffered an anastomotic leak to be €44,268 (€20,792 higher than when the patient suffer no complications) (13).

3. BioGlue is already used, licensed and has been shown to be safe

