6. AIMS AND OBJECTIVES

This study aims to investigate if the use of BioGlue, in addition to standard technique, is technically feasible and safe to provide evidence to allow for a larger randomised controlled study with the aim of investigating the effect on anastomotic leaks.

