7. STUDY DESIGN

7.1 Summary of Study Design

This is a feasibility study to investigate the use of BioGlue (a mix of purified bovine serum albumin (BSA) and glutaraldehyde) to reinforce the anastomosis created during a minimally invasive oesophaegectomy. The study will be undertaken at a single centre and consecutive patients will be included up to a total of 30. Patients will receive the standard follow up following oesophagectomy, with a telephone consultation one week after discharge and then clinic appointments at two- and six-weeks. For the purposes of the study, all participants will also be reviewed by the study team six-weeks after the day of surgery. Patients will then continue to be followed up as normal, but outside of the bounds of this study.

The results from this study can guide the researchers in the further use of this product in the wider context of a randomised controlled trial.

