14.5 Interim analysis and criteria for early study termination

As this is a feasibility study assessing the ease and safety of application of the glue, there will be no planned interim analysis. Due to the small number of patients needed for the study, and the acceptable leak rate of 20%, it is entirely possible that consecutive participants suffer an anastomotic leak through chance alone. Each anastomotic leak will be reviewed as a serious adverse event. If there are any concerns that a leak has been caused by the BioGlue applied (for example, the anastomosis has become abnormally adherent to structures in the chest at re-operation) then a serious adverse device effect has occurred, and the study paused while this is reviewed. If there are 5 consecutive anastomotic leaks in a row, this will trigger an internal review and an independent data monitoring committee formed and convened to review the study. If there are more SAEs than expected, raised by the research team inputting data, this will be highlighted to the PI. Early termination of the study can then be considered by the PI.

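### Section 14.2 gives five binary outcomes only a standard error at n=30; this is zero or misleading when events are absent or few, though adequate at the documented 20% leak rate

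*Protocol*

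**What the plan says.** Protocol section 14.2 lists five yes/no outcomes: anastomotic leak, death from any cause within six weeks, and unplanned return to ITU, to theatre and to the surgical high care unit. For these it fixes one reporting rule: "In all cases the proportion in each category will be reported, along with the standard error for the proportion". It names no confidence interval, and none appears elsewhere in the protocol. For Clavien-Dindo grade, number of CT scans and antibiotic use it names proportions (with a median duration for antibiotics) but no measure of precision.

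On size, section 7.1 says "consecutive patients will be included up to a total of 30". On purpose, section 6 asks whether the technique "is technically feasible and safe to provide evidence to allow for a larger randomised controlled study", and section 14.2 adds: "Secondary endpoints will be described appropriately for use in informing future controlled analysis".

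Leak is the only one of the five with a stated rate. Section 4 says "Leak rates from the gastro-oesophageal anastomosis are quoted by NICE as 20"%, and section 14.5 refers to "the acceptable leak rate of 20"%.

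**The concern.** The standard error of a proportion is estimated from the observed proportion itself, so it shrinks towards zero as the observed count does. With no events it is exactly zero, whatever the sample size. A line reading 0% with a standard error of 0 suggests certainty, yet 30 patients cannot exclude a material risk. With one to three events, a reader who adds and subtracts about two standard errors gets a lower limit below zero and an upper limit that is too low. For a safety outcome the upper limit is the one that matters.

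This has some weight here because the study has no comparator and no test, and its primary endpoint is qualitative. The uncertainty around these proportions is most of what the study can say numerically about safety to those planning the later randomised trial. The rule is also a choice that the protocol makes and applies to all five outcomes, not a detail that it leaves open.

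**Working it through.** **Inputs.** n = 30 (section 7.1). Leak rate 20% (sections 4 and 14.5). The protocol gives no overall rate for death or for any unplanned return. It states no precision target and no sample-size derivation, so there is no figure of its own to reproduce.

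**Formulas.** With x events and p = x/n:
- SE = sqrt(p(1-p)/n), and the interval a reader would build from it is p ± 1.96 SE.
- Exact (Clopper-Pearson) limits are the 2.5% quantile of Beta(x, n-x+1) and the 97.5% quantile of Beta(x+1, n-x). At x = 0 the upper limit is 1 - 0.025^(1/30) = 11.6%.
- Coverage is the binomial probability, summed over x = 0 to 30, of the counts whose interval contains the true rate.

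**Results by observed count.** For example, at x = 1, SE = sqrt(0.0333 × 0.9667 / 30) = 3.3%, and 3.3% ± 1.96 × 3.28% gives -3.1% to 9.8%.

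| x/n | SE | p ± 1.96 SE | Exact 95% | Wilson 95% |
|---|---|---|---|---|
| 0/30 | 0.0% | 0 to 0 | 0 to 11.6% | 0 to 11.4% |
| 1/30 | 3.3% | -3.1% to 9.8% | 0.1% to 17.2% | 0.6% to 16.7% |
| 2/30 | 4.6% | -2.3% to 15.6% | 0.8% to 22.1% | 1.9% to 21.3% |
| 3/30 | 5.5% | -0.7% to 20.7% | 2.1% to 26.5% | 3.5% to 25.6% |
| 6/30 | 7.3% | 5.7% to 34.3% | 7.7% to 38.6% | 9.5% to 37.3% |

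From 0 to 3 events, the upper limit implied by the SE falls short of the exact one by about 6 to 12 percentage points.

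**Results by true rate.** P(0 events) = (1 - rate)^30.

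| True rate | P(0 of 30) | Coverage of p ± 1.96 SE | Coverage of exact interval |
|---|---|---|---|
| 1% | 74% | 26% | 99.7% |
| 2% | 55% | 45% | 97.8% |
| 3% | 40% | 60% | 98.8% |
| 5% | 21% | 78% | 98.4% |
| 10% | 4% | 81% | 99.2% |
| 20% | 0.1% | 94.6% | 98.0% |

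**How likely is a zero count for death?** This needs an assumption. Section 4 says "Increases in mortality ranging from 18.2-35% have been quoted in the literature". If that is read as the absolute extra risk of death after a leak, then 20% × 18.2% = 3.6% and 20% × 35% = 7.0%. These give 0.9636^30 = 33% and 0.93^30 = 11% for no deaths in 30. At an assumed 3% the figure is 0.97^30 = 40%. Over an assumed 3% to 7%, a reported SE of zero for mortality therefore has a probability of about 40% to 11%.

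**The case against.** A reader might infer that all the safety results, leak included, will look far more certain than they are. The documents do not support that. Leak is the one outcome with a stated rate. At 20% the interval built from the SE covers 94.6%, its limits at 6/30 differ from the exact ones by 2 to 4 points, and a zero count has probability 0.1%. The leak estimate taken into trial planning would carry a serviceable measure of uncertainty.

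A reader might also infer that these are outcomes in which only 0 to 3 events are expected. For leak at 20%, the chance of 3 or fewer in 30 is about 12%. For the unplanned returns the protocol gives no rates, and section 4 says that a leak can itself lead to a return to theatre or ITU, so near-zero counts cannot be presumed.

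Three further points are fair. The protocol plans a standard error, not p ± 1.96 SE, so the negative limits and low coverage belong to an interval that a reader might build but the protocol does not commit to. No test, threshold or stopping rule uses the SE: the objectives are to describe and quantify, and the review triggers in section 14.5 rest on events. Finally, anyone who knows the proportion and n can recover x and compute an exact interval.

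All of this limits the consequence. It does not rescue the rule for sparse outcomes: an SE of zero at 0/30 misstates precision without any further construction, and a report should not depend on its readers to repair it.

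**Conclusion.** The point holds for any of the five binary outcomes that turns out to have zero or few events, most plausibly six-week mortality. There the only measure of precision that the protocol fixes is either 0, against an exact upper limit of 11.6%, or invites an interval that is too low at both ends. It does not hold for leak at about the documented rate. Severity is minor: the outcomes are descriptive, nothing is decided on the SE, and the information can be recovered.

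The limits in the first table assume only n = 30 and the usual SE formula. The probability of a zero count for death rests on an assumed 3% to 7% mortality, which the protocol does not state. Only the protocol is at hand. A separate analysis plan might add intervals, but that would not change what section 14.2 prescribes.

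**What to change.** In Protocol section 14.2, for the five binary endpoints, replace the clause that calls for the standard error with: x/n and an exact (Clopper-Pearson) or Wilson 95% confidence interval. Choose one method and name it. Zero events would then be reported with their upper limit, about 12% if n = 30 (11.6% exact, 11.4% Wilson).

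The change needs no extra data, patients or design work, and section 14.4 already allows documented minor alterations to the analysis plan. The only downside is that the reported uncertainty becomes wider and asymmetric for sparse outcomes.
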